3.1 General Design

The cardiovascular effects of Adderall, prescription medication often abused by students for non-medical purposes, are not well understood. This is a pilot study to investigate the cardiovascular and metabolic response to taking an oral dose of Adderall (25 mg) by healthy adults. Subjects will be studied using a randomized, double-blind, placebo-controlled, crossover design with two separate experimental sessions: Adderall and placebo pill; studies will be performed on 2 separate study days, each study lasting from 6-8 hours.

[figure not shown]
Active drug: Oral Generic Adderall: total of 25 mg dose. This dose will be compounded by Pharmacy. The compounded dose will contain: [dextroamphetamine sulfate 6.25 mg, dextroamphetamine saccharate 6.25 mg, amphetamine aspartate monohydrate 6.25 mg, amphetamine sulfate 6.25 mg (equivalent to amphetamine base 15.73 mg)].

Placebo drug: Placebo designed by CRTU Research Pharmacist team

Adderall and placebo drug will be prepared by research pharmacists in similar capsule form. Placebo pill is carefully designed by our team of CRTU Research Pharmacists to match the prescription medication, Adderall. Both drugs will be given in an identical manner so that participants and study investigators are not aware of which drug is being administered. Subjects will remain unaware of the nature of the drug administered on each study day throughout the study. Each experimental session (Adderall and placebo pill) will be conducted using the same protocol, in a random order.

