Study participants will be recruited and offered participation in this trial as described in other sections of this protocol. Interested qualified participants will be consented. The study will be performed at St Marys CRTU on two separate days minimum 5 days apart. Participants will be consented upon arrival to the CRTU and will be consented by the Research Staff. The start time of the studies will be the same. Participants will be fasting 4 hours prior to the study and will be asked to abstain from all stimulants, including caffeine and alcohol for at least 24 hours prior to initiation of this study. When presenting to the CRTU on the first day of the study, participant's height and weight will be obtained by the CRTU staff. On each study day, CRTU personnel will perform urine pregnancy test if needed. If positive pregnancy test, participant will not be able to participate in the study. The research staff will obtain waist and hip and bioimpedance measurements (described below); the participant, together with the research staff, will fill out several questionnaires regarding cardiovascular health and dietary habits (attached with application). Subsequently, the participants will take part in research studies as outlined below. Baseline measurements will be obtained at rest. After the end of baseline recordings, the subjects will be given 25 mg oral dose of Adderall vs placebo pill. The second set of measurements will be obtained starting 3 hours after taking the pill, using similar protocol as at baseline.

We expect to enroll approximately 25 healthy subjects.

Schematic diagram (flowchart) of study events:

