5.3 Method for Assigning Subjects to Treatment Groups

The proposed research study is a randomized, double-blind, placebo-controlled clinical trial. The randomization list will be computer generated. We will utilize a randomized block design, with a block size of 6, considering enrolling 30 subjects, each completing two study days. This assures balance between the treatment arms after each group of 6 subjects. Subjects and study personnel will be blinded to the nature of the pill administered on each study day.

Randomization will be performed by CTSA statistician. De-identified coded spreadsheet will be provided to the research pharmacist who will be distributing the drug/placebo.

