4. CRTU personnel will obtain height and weight of the participant. CRTU personnel performs urine pregnancy test as needed (Urine collection #2). If the participant is pregnant, then the participant is unable to participate in the study, and will receive \$25.00 for their time. In all participants at least 100 ml of urine may be collected for future biomarker analysis at baseline and
5. Participant will be asked to fill out the following questionnaires on a Mayo laptop or on paper. Some of these questionnaires may be administered more than once: Food Scale, Symptoms Questionnaire, and Sleepiness Scales.
6. CRTU Staff will insert peripheral IV line into the forearm and blood draw #1 will be obtained after at least 30 minute rest.
7. Study personnel will obtain BP and HR measurements in supine position. Measurements will be taken every 1-3 minutes throughout the study.
8. Study personnel will be obtaining 12-lead ECG recording throughout the study.

9. Study personnel will perform paced breathing test, details described in the IRB Protocol. Breathing will be measured by elastic bands around the chest and abdomen.
10. Baseline endothelial function test will be performed by the study team.
11. Study personnel will perform orthostatic BP and HR measurements.
12. Study personnel blinded to the study will give the participant the study drug vs placebo drug (one not received on Day 1), according to the randomized, double-blind, placebo-control crossover design of this study.
13. Study subject will be asked to rest in sedentary or recumbent position for 3 hours.
14. CRTU Staff will do blood draw #2 after 30 minutes of supine resting at 3 hours after intake of active drug/placebo drug.
15. The 12-lead ECG recording continues on.
16. Study personnel will perform post-intervention paced breathing test, details described in the IRB Protocol. Breathing will be measured by a elastic bands around the chest and abdomen.
17. Post intervention endothelial function test will be performed by the study team.
18. Post intervention ultrasound of the heart may be performed by the study team or echo lab personnel..
19. Study personnel will perform orthostatic BP and HR measurements.
20. Study personnel will describe the series of stress tests that will follow and BP, HR, ECG measurements will continue through the stress tests.

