7.1 Sample Size Determination

Anticipating to study 30 subjects, we will have 80% power to detect a significant increase in the blood parameters (i.e. BP, HR etc.) for the study drug as compared to the placebo drug, with a 2-sided significance level of 0.05. Specifically, we are powered to detect an effect size of 0.80, which is a difference in the means between the different types of drugs (study vs. placebo) that is 80% of the standard deviation. For example, we are powered to detect an increase of 5% in the blood parameters for the study drug vs. only a 1% increase for the placebo drug (4% difference), assuming a standard deviation of 5% (effect size = 0.80).

Data Analysis Plan: Plan is to analyze data using two-way analysis of variance (ANOVA) for repeated-measures with time (before vs after drug intake) as the within factor and group (study drug vs placebo drug) as the between factor. The key variable will be the group-by-time interaction. Differences in hemodynamics (BP, HR) before and after consumption of a drug will be determined by repeated measures ANOVA. Student *t* test (paired or unpaired) will be used for between group comparisons with respect to change in given variable. $P < 0.05$ will be considered statistically significant. Data will be expressed as mean \pm SEM.

Endpoints:

Primary Endpoint:

- 1) Determine the hemodynamic changes (magnitude of BP and HR response) in healthy adults after taking one dose of prescription medication Adderall 25 mg orally, one time, and compare these responses to those after a placebo pill

Secondary Endpoint:

- 1) Determine ECG changes and incidence of arrhythmias after consumption of Adderall compared to baseline ECG
- 2) Determine if consumption of a dose of Adderall is associated with altered neurohormonal and cardiovascular activation, assessed by measurements of biomarkers, such as catecholamines before and after Adderall/placebo intake
- 3) Determine if taking Adderall induces orthostatic changes
- 4) Assess baroreflex sensitivity (paced breathing) before and after Adderall vs placebo intake
- 5) Determine the effect of Adderall on cardiovascular hemodynamics during stress conditions including mental stress (arrhythmics), physical stress (sustained hand grip) and pain stress (cold pressor stress) as compared to measurements at rest
- 6) Determine the changes in heart function and brachial artery reactivity after Adderall intake using an ultrasound

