7.2 Statistical Methods

Descriptive Statistics

Univariate descriptive statistics and frequency distributions will be calculated, as appropriate for all variables. Baseline values for demographic, clinical, and outcome variables (primary and secondary) will be tabulated for both groups (i.e., study drug vs placebo drug). Data will be inspected before analysis for the need of transformations to reduce the possible impact of outliers in skewed distributions, and transformed accordingly. Distributions across subgroups used in randomization will also be compared to assess whether the randomization was successful in equalizing distributions of these prognostic variables across treatment groups. Putative prognostic variables that will be investigated through these descriptive analyses include variables such as BP, HR, age, gender, BMI, baroreflex sensitivity, catecholamine responses.

Handling of Missing Data

We expect missing data to be minimal. However, some subjects may drop out from the two study day protocol. The two-day longitudinal model is flexible to allow available data to be analyzed, for instance, if a subject completes the first study day, but not second study day. These models assume ignorable (MCAR/MAR) missingness. Sensitivity analyses may be performed to assess the robustness of these assumptions.

Multiplicity

There is no need to account for multiple comparisons in this study. With only 30 subjects, no correction for multiple comparisons using Bonferroni or Tukey's procedure will be necessary.

Primary Hypothesis: We hypothesize that BP and HR increase after intake of study drug compared to placebo.

Data will be analyzed using two-way analysis of variance (ANOVA) for repeated-measures with time (before vs after drug intake) as the within factor and group (study drug vs placebo drug) as the between factor. The key variable will be the group-by-time interaction. Differences in hemodynamics before and after consumption of a drug will be determined by repeated measures ANOVA. Student *t* test (paired or unpaired) will be used for between group comparisons with respect to change in given variable. $P < 0.05$ will be considered statistically significant. Data will be expressed as mean \pm SEM.

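### Drug versus placebo is analysed as a between-subject factor although every subject takes both pills, so the key test ignores the pairing

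*Combined protocol and SAP*

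**What the plan says.** Section 3.1 sets the design: "Subjects will be studied using a randomized, double-blind, placebo-controlled, crossover design with two separate experimental sessions: Adderall and placebo pill". Section 5.3 plans on "considering enrolling 30 subjects, each completing two study days", and section 6.2 gives each subject on Day 2 whichever pill was not taken on Day 1.

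For the primary hypothesis, section 7.2 names a two-way repeated-measures ANOVA "with time (before vs after drug intake) as the within factor and group (study drug vs placebo drug) as the between factor", with the group-by-time interaction as the key variable. The Data Analysis Plan in section 7.1 and Secondary Hypothesis 1 in section 7.2 repeat this. Each adds a Student t test on change that may be paired or unpaired, with no rule for choosing. The missing-data paragraph refers to a two-day longitudinal model that is not defined anywhere. No period or sequence term appears.

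On sample size, section 7.1 states: "Anticipating to study 30 subjects, we will have 80% power to detect a significant increase in the blood parameters". The inputs are two-sided 0.05, an effect size of 0.80, and a 5% versus 1% increase with an SD of 5%. Section 3.1 gives another number: "We expect to enroll approximately 25 healthy subjects".

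**The concern.** Each subject supplies a change on drug and a change on placebo, so the treatment comparison is made within subjects. Declaring treatment a between factor treats the two days of one person as two unrelated people. If the two changes are positively correlated, the interval is too wide and the test conservative. If they are negatively correlated, false positives rise. Width matters because the primary objective is the magnitude of the BP and HR response.

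The open t test does not settle the matter, since a paired and an unpaired test can fall on different sides of 0.05. Two related gaps sit in the same text. The ANOVA and t-test template is also applied to the frequency and severity of ECG findings, which are not continuous. Section 7.1 does not say whether the 5% is the SD of each change or of the within-subject difference.

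**Working it through.** **1. The plan's own figure.** The inputs from section 7.1 are a difference of 5% - 1% = 4 points, SD 5% (4/5 = 0.80) and two-sided alpha 0.05. Power comes from the noncentral t distribution.

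- Unpaired, 30 + 30: noncentrality 0.80 × √(30/2) = 3.10, 58 df, power 86.1%.
- Paired, 30 subjects, 5% as SD of the difference: 0.80 × √30 = 4.38, 29 df, power 98.8%.
- Unpaired, 25 + 25: 0.80 × √(25/2) = 2.83, 48 df, power about 79%; 26 + 26 gives about 81%.

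The stated 80% is not reproduced with 30 subjects on either reading of the SD. It fits an unpaired calculation on about 25 per condition, close to the number in section 3.1. That link is an inference.

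**2. What the key test is.** With two time points and treatment as a between factor, the interaction F equals the squared unpaired t on the change scores. With treatment as a within factor it equals the squared paired t. On one simulated data set these were 13.02 and 20.50 respectively.

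**3. Effect of ignoring the pairing.** Let σ be the SD of each change and ρ the correlation between a subject's two changes.

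- True SE of the treatment difference: σ√(2(1 - ρ)/n).
- SE used by the planned test: σ√(2/n), whatever ρ is.
- Planned 95% half-width, σ = 5, n = 30: 2.002 × 5 × √(2/30) = 2.58 points.
- Within-subject half-width with a period term (28 df): 2.048 × 5 × √(2(1 - ρ)/30). At ρ = 0.5 this is 2.048 × 0.913 = 1.87 points.

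The documents give no ρ, so a range is assumed. Type I error and power come from 200,000 simulated trials per scenario (bivariate normal changes, 15 subjects per sequence, SD of each change 5%).

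| ρ (assumed) | Type I error, planned | Half-width, planned | Half-width, within | Power at 4 points, planned | Power at 4 points, within | Power at 2.5 points, within |
|---|---|---|---|---|---|---|
| 0 | 5.0% | 2.58 | 2.64 | 86% | 85% | 46% |
| 0.1 | 4.0% | 2.58 | 2.51 | 87% | 88% | 50% |
| 0.2 | 2.9% | 2.58 | 2.37 | 89% | 92% | 55% |
| 0.3 | 2.0% | 2.58 | 2.21 | 90% | 95% | 61% |
| 0.5 | 0.7% | 2.58 | 1.87 | 93% | 99% | 75% |
| 0.7 | 0.1% | 2.58 | 1.45 | 97% | >99% | 93% |

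The within-subject test holds about 5% throughout. At the illustrative 2.5 points the planned test has 46-48% power at every ρ shown. At ρ = -0.3 its type I error is 8.5%, and the correct half-width is 3.02.

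**4. Other readings of the inputs.**

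- With 25 subjects and 4 points, at ρ = 0, 0.2 and 0.5: planned power is 79%, 82% and 87%; within-subject power is 77%, 85.5% and 97%.
- If 5% is the SD of the within-subject difference and n = 30, planned power at 4 points is 93-99% up to ρ = 0.5 and 76% at ρ = 0.7; within-subject power is 99%.

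**5. The open t test.** Always reporting the more favourable version gives a type I error of at most 5.8% for ρ ≥ 0. With 30 subjects and SD 5% per change, the two versions disagree on P < 0.05 in 3-6% of trials at 4 points. At 2.5 points they disagree in 6%, 9% and 28% of trials at ρ = 0, 0.2 and 0.5.

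**The case against.** The plan does allow a paired t test, and its two-day longitudinal model suggests that a subject-level analysis was in mind. So the pairing is lost in the key ANOVA, not in every test the plan permits. That is correct as a description. But the paired version is only one of two permitted options, the longitudinal model is never specified, and the interaction remains the named key test.

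The size of the harm rests on a correlation the documents do not give. It may be modest, because same-day baselines are already subtracted. At ρ = 0 the within-subject interval is slightly wider, and at 0.1 the gain is small. The large power gains need both a sizeable correlation and a true difference below the 4-point target. For a study that calls itself a pilot, this is mostly a precision question. All of that stands and limits the severity.

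The power statement errs on the safe side, since both readings at 30 subjects exceed 80%. Recruiting 30 to obtain about 25 completers would also fit, though the documents do not say so. The power statement and the non-continuous ECG outcomes are separable from the pairing defect, but they sit in the same text and can be corrected with it.

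**Conclusion.** The concern holds: the key test does not match the crossover design, and nothing else in the plan repairs it. With balanced sequences the estimate is unbiased; the error lies in the interval and the P value. On the reading that 5% is the SD of each change, with 30 subjects, the planned interval is 2.58/1.87 = 1.38 times as wide as it need be at ρ = 0.5, 2.58/2.37 = 1.09 times at ρ = 0.2, and marginally too narrow at ρ = 0. The nominal 5% level is exact only at ρ = 0. On that same reading the 4-point target keeps at least 86% power for every ρ ≥ 0, so the trial is not put at risk. This should be fixed before analysis. Every figure that depends on ρ rests on an assumed value. That the stated 80% power does not reproduce at 30 subjects needs no assumed ρ.

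**What to change.** Amend the Study Summary, the Data Analysis Plan in section 7.1 and both hypothesis paragraphs in section 7.2 so that treatment is a within-subject factor.

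- **Outcomes measured before and after dosing** (BP, HR, orthostatic measures, continuous ECG intervals, catecholamines, baroreflex sensitivity, brachial reactivity): a linear mixed model on change from that day's pre-dose value, with fixed treatment, period and sequence and with subject as the random unit. Report the treatment contrast with a 95% CI and name the small-sample degrees-of-freedom method.
- **Covariance:** use a within-subject structure that can be negative, for example unstructured. A random intercept truncated at zero would not protect the test (type I error 5.8% at ρ = 0 and 8.5% at -0.3).
- **Stress tests:** the same model on each day's stress-minus-rest response.
- **Food intake and heart ultrasound:** the same model on the post-dose value. Assign appetite scores explicitly to one of these models.
- **Arrhythmia incidence and the frequency or grade of ECG findings:** a paired method for binary or ordinal data. A mixed logistic or ordinal model keeps subjects with one visit; McNemar's test does not.
- **t test and missing data:** delete the unpaired option, and name the mixed model as the two-day longitudinal model.
- **Section 7.1:** say which SD the 5% is, restate the power to match, and reconcile 30 subjects with about 25.

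The cost is wording only, with no added subjects or data. The period term takes one degree of freedom (half-width 1.867 to 1.870 points at ρ = 0.5). If ρ is zero the correct interval is slightly wider than planned (2.64 against 2.58 points), and wider still if ρ is negative.

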4.4 Early Withdrawal of Subjects

4.4.1 When and How to Withdraw Subjects

Subject participation in this study is completely voluntary. Subjects can withdraw their consent and discontinue participation in the study at any time without affecting their relationship with Mayo Clinic doctors or Mayo Clinic. Although we do not anticipate high withdrawal rates in our healthy study population, rare possible reasons for withdrawal from this protocol is if subject becomes suddenly concerned about the safety or side effects of the study drug. This type of

withdrawal could be prevented by clear disclosure of the potential side effects of Adderall to the subject prior to enrollment. However if such situation does occur, subject will be allowed to discontinue participation in the two day study protocol.

Subject participation in this study may be ended by the principal investigator if it is felt it is in the best interest of the subject, if subjects do not follow the study procedures, or if the study is stopped.

Subjects will not need to be replaced per-se; enrollment of subjects will continue until desired number of participants is completed. There is no long term follow up in this study protocol.

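### The order of the two study days is randomised, but no stated analysis includes a visit (period) term, so a visit difference in the analysed outcome stays in the error and can shift the drug estimate if completers are unequal between orders

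*Combined protocol and SAP*

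**What the plan says.** Section 3.1 of the combined protocol and SAP describes a two-session crossover: "Each experimental session (Adderall and placebo pill) will be conducted using the same protocol, in a random order". Section 5.3 sets the allocation: "We will utilize a randomized block design, with a block size of 6, considering enrolling 30 subjects, each completing two study days", and adds "This assures balance between the treatment arms after each group of 6 subjects".

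Sections 7.1 and 7.2 give the analysis as a two-way repeated-measures ANOVA with "time (before vs after drug intake) as the within factor and group (study drug vs placebo drug) as the between factor". Section 7.2 repeats it for Secondary Hypothesis 1. On the target of inference it says "The key variable will be the group-by-time interaction". A Student t test, paired or unpaired, "will be used for between group comparisons with respect to change in given variable".

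No factor in these descriptions is visit, day, period, sequence or order. Under missing data, Section 7.2 says "The two-day longitudinal model is flexible to allow available data to be analyzed", but lists no terms for that model. The same section compares distributions across randomisation subgroups, which is descriptive and adjusts nothing.

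On withdrawals, Section 4.4.1 says "enrollment of subjects will continue until desired number of participants is completed". It makes no provision for order balance among those who complete.

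**The concern.** In a two-period crossover, each subject's drug-minus-placebo difference contains the drug effect plus or minus any visit effect, with the sign set by the order. Pairing does not remove this. Even a correct paired t test leaves the visit effect in the SD of the differences, so the point is separate from the paired-or-unpaired question.

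The visits are not identical. Under Sections 6.1 and 6.2, visit 1 carries consent, the Cardiovascular Research Data Sheet and eight questionnaires, against three at visit 2. It is also the subject's first encounter in the trial with the timed arithmetic, handgrip and ice water.

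Two things are at stake: an error term that is too large, which costs power, and a shifted drug estimate when the orders are unequal among completers. Blocks of 6 balance order among those randomised, not among those who finish.

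What counts as a visit effect depends on the outcome. For BP and HR change, only a visit difference in the pre-to-post change matters. For food intake, recorded only at the end of the day, the level itself matters.

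**Working it through.** **Inputs from the plan.** N = 30, two-sided alpha 0.05, 80% power, 4-point difference (5% against 1%), SD 5%, effect size 0.80 (Section 7.1); blocks of 6, hence 15:15 if 30 are randomised (Section 5.3).

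**Assumptions, not in the documents.** Visit effect π (visit 2 minus visit 1, in the analysed outcome) of 1 to 4 points. SD of the within-subject drug-minus-placebo difference s = 5; Section 7.1 does not say which SD its 5% is.

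**The plan's own figure.** The stated 80% does not come back at N = 30. A paired t test with s = 5 gives 98.8%. A two-sample t test gives 86% with 30 observations per condition and 56% with 15 per arm. About 80% arises with 25 to 26 independent observations per condition (79% and 81%). The point below does not depend on this figure.

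**Mechanism.** Let τ be the drug effect. The paired difference has mean τ − π in the drug-first order and τ + π in the placebo-first order.

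**Equal orders (15:15).** The visit effect cancels from the mean. The expected sample variance of the differences becomes s² + π²·n/(n − 1). The true SE is 5/√30 = 0.913.

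- π = 1: 25 + 1 × 30/29 = 26.03; √(26.03/25) = 1.020
- π = 2: 25 + 4 × 30/29 = 29.14; √(29.14/25) = 1.080
- π = 4: 25 + 16 × 30/29 = 41.55; √(41.55/25) = 1.289

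Simulation of the paired t test without visit (the values for π = 0 are exact; simulated type I errors carry an uncertainty of 0.1 to 0.2 points):

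| π | Estimated SE inflated by | Type I error | Power at 4 points |
|---|---|---|---|
| 0 | 0 | 5% | 98.8% |
| 1 | 2% | about 4.6% | about 98.6% |
| 2 | 8% | about 3.4% | 98.3% |
| 4 | 29% | about 1.3% | about 95.4% |

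The sampling SD of the estimate stays near 0.91 throughout. Only the estimated error grows, so the test is conservative. For a smaller true effect of 2.5 points, power falls from 75% to 70% (π = 2) and 54% (π = 4).

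**Sensitivity to the SD.** If 5% is the SD of each change and the two changes correlate at ρ, then s = 5√(2(1 − ρ)), which is 7.07, 5.00 and 3.87 for ρ = 0, 0.5 and 0.7. At π = 4 the inflation is 15%, 29% and 45%.

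**Unequal completers.** Bias = π(n_placebo-first − n_drug-first)/(n_placebo-first + n_drug-first). With the placebo-first order short:

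- 15 drug-first, 12 placebo-first: −3/27 = −0.11π
- 15 drug-first, 10 placebo-first: −5/25 = −0.20π

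At 15:10 and π = 4, a true 4.0 is estimated as 4.0 − 0.8 = 3.2, with power 71%. With visit in the model the estimate is 4.0 and power 96%. The sign reverses if the other order is short.

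**Day-1-only data in an unpaired comparison.** The bias is π times the difference in visit-2 share between the drug and placebo data. At 15:12 it is 12/27 − 15/30 = −0.06; at 15:10 it is 10/25 − 15/30 = −0.10. This is half the completer figure.

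**False positives.** With no drug effect and π = 4, simulated two-sided type I error without visit is 2.1% at 15:12 and 4.3% at 15:10. The inflated error offsets the bias.

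**Level shifts.** Adding 10 units to both the pre-dose and post-dose values of one visit left the t statistic for change unchanged.

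**The case against.** The strongest reply is that little is lost where the trial is powered. At 4 points and 15:15, power stays at about 95% or more across the assumed range. That stands.

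The visit effect is assumed, and it must act on the change. Section 7.1's example placebo change is only 1%, so a 4-point visit effect equals the whole planned drug difference. This also stands, and it is why the range here starts at 1 point. Common start time, fasting and stimulant abstention (Sections 3.1, 6.1 and 6.2) make a large effect less likely, but do not exclude one.

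The SE figures are for a paired analysis. Taken literally, with drug as a between factor and an SD of 5 per change, visit adds π²/4 to the variance. Inflation is then √(1 + 1/25) = 1.02 at π = 2 and √(1 + 4/25) = 1.08 at π = 4. That is correct, but it reflects an error term that ignores the pairing, which is a separate defect.

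The 15:10 split is strained: Section 7.2 expects minimal missing data, and Section 4.4.1 does not anticipate high withdrawal. Section 7.3 also defines an all-randomised population, so day-1 data may be kept and the bias halved. Both stand.

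A reader might infer that stress-test results carry the full visit effect. Sections 3.3 and 7.1 define them against rest, so a shift common to rest and stress cancels.

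Finally, the two-day longitudinal model might contain visit. Its terms are not listed, so this cannot be confirmed.

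**Conclusion.** The omission is real: a crossover with randomised order has no visit term in any analysis whose terms are stated. The consequence is mainly lost efficiency. For a paired analysis at 15:15, with s = 5 and a visit effect of 1 to 4 points in the analysed outcome, the SE is overstated by about 2 to 29%. The cost at the planned effect is at most about 3.4 points of power (98.8% − 95.4%), and more for smaller effects. Secondary outcomes have no stated power, so the comfortable margin at 4 points cannot be assumed for them. Bias arises only with unequal completers: 0.11 of the visit effect at 15:12, 0.20 in the extreme 15:10 case, and about half that if day-1-only data enter an unpaired comparison.

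Three stronger readings are not supported. The trial is not shown to be underpowered for its planned effect on this ground. False positives are not inflated in the scenarios examined. Nor does every difference between visits matter, since a level shift shared before and after dosing drops out of the change. The visit effect and the paired SD are assumptions throughout.

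**What to change.** In Section 7.2, for the primary and all continuous secondary analyses, specify a within-subject model of the pre-to-post change, or of the post-dose value where there is no baseline. Use drug and visit (1 or 2) as fixed effects and subject as a random effect; order may be added. For subjects with both days, an equivalent form compares the visit 1 minus visit 2 difference between the two order groups; half the difference between group means is the drug effect. List the same terms for the model used with incomplete data, and report completers by order.

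The order is already on the randomisation list, so no new data are needed. The cost is one degree of freedom (29 to 28). If there is no visit effect, power changes by about 0.1 percentage point at 15:15. With unequal completers the cost is slightly higher: the variance goes from s²/n to (s²/4)(1/n₁ + 1/n₂), which at 15:10 is 25/25 = 1.00 against 6.25 × (1/15 + 1/10) = 1.04, or about 2 points of power for a 2.65-point effect. The wording should be settled before unblinding.
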